8.6. Randomization and Blinding

8.6.1. Randomization

This is an open-label study and therefore randomization is not applicable.

8.6.2. Blinding

This is an open-label study and therefore the clinical drug supplies are not blinded.

9. STUDY DRUG MATERIALS AND MANAGEMENT

9.1. Study Drug

The study medication is A-101 (Hydrogen Peroxide) Topical Solution, 40% (w/w). The study medication is a clear, colorless solution.

9.2. Study Drug Packaging and Labeling

A-101 (Hydrogen Peroxide) Topical Solution, 40% (w/w) will be provided by Aclaris Therapeutics, Inc. and labeled according to the local law and legislation.

The study medication will be packaged in single use applicators. Each single-use applicator consists of a crushable glass ampoule that contains 2.2 milliliters (mL) of study medication that provides for at least 1.3 mL of study medication available for treatment. The ampoule is provided inside a sealed polyethylene tube with a flocked, doe foot applicator on one end.

9.3. Study Drug Storage

Investigational sites will be supplied with open-label stock of A-101 40%. Investigational study medication supplies are only to be used for subjects properly consented and enrolled to this study.

A-101 40% must be stored in a location where there is limited access to the investigational study medication at 59°F to 77°F (15°C to 25°C) excessive heat, open flame and combustibles, in a well-ventilated, dry area. Excursions from these temperature ranges must be reported to Aclaris Therapeutics, Inc.

9.4. Study Drug Preparation

Activated applicators are stable for 4 hours at room temperature (59°F to 77°F or 15°C to 25°C).

9.5. Administration

The subject will receive up to 4 applications to each target or non-target SK at Visit 2, and if the subject meets retreatment criteria, at Visit 5 and Visit 7.

Apply study medication to each target and non-target SK for approximately 20 seconds. Allow each target and non-target SK to remain undisturbed for approximately 60 seconds. Repeat the application/waiting cycle until the study medication has been applied to each target and non-target SK up to 4 times. Subjects may receive up to 3 treatments (Visit 2, Visit 5 and Visit 7).

9.6. Study Drug Accountability

The investigator or designee will maintain an accurate record of the receipt of the study medications as shipped by Aclaris Therapeutics, Inc. (or designee), including the date received and the condition of the study medications. One copy of this receipt will be returned to Aclaris Therapeutics, Inc. (or designee) when the contents of the study medication shipment have been verified and one copy maintained in the study file. In addition, an accurate study medication disposition record will be kept, specifying the amount dispensed for each subject and the date of dispensing. This inventory record will be available for inspection at any time. At the completion

of the study, the original inventory record will be available for review by Aclaris Therapeutics, Inc. upon request.

Final drug accountability will be completed by the study monitor at the completion of the study and all unused study medication will be returned to Aclaris Therapeutics, Inc. drug depot for disposal per Aclaris Therapeutics, Inc. (or designee's) written instructions.

9.7. Study Drug Handling and Disposal

Nitrile or vinyl examination gloves must be worn during the application process. *Latex gloves are prohibited.*

10. ASSESSMENT OF EFFICACY

Similar lighting conditions and subject positioning should be used for all evaluations for a given subject.

10.1. Target SK Identification

At Visit 1, the investigator will identify up to 7 Seborrheic Keratoses on each subject for treatment and evaluation. Three (3) target lesion must be identified, and up to 4 non-target lesions may be identified. Two (2) target SKs must be on the face, and the additional 1 target SK must be on the neck, or décolletage. Up to 4 additional non-target lesions may be on the face, neck, or décolletage.

Face:

- Vertically from the mandibular ridge vertically up to the hairline (for subjects with a receded hairline the hairline is defined by the vertical line drawn coronally from tragus to tragus)
- Horizontally from tragus to tragus, excluding the eyelids and areas within 5mm of the orbital rim.

Neck:

- Vertically from the mandibular ridge vertically down to the top of the collar bone

Décolletage:

- From the collar bone down including the shoulders and cleavage area

At Visit 1, each target SK must:

- Have a clinically typical appearance
- Have a PLA of ≥ 2
- Have a diameter between 5 to 15 mm
- Be a discrete lesion (no overlapping lesions)
- Not be covered with hair which, in the investigator's opinion, would interfere with the study medication treatment or the study evaluations (NB: the study medication may bleach hair)
- Not be in an intertriginous fold
- Not be on the eyelids
- Not be within 5mm of the orbital rim
- Not be pedunculated.

At Visit 1, each non-target SK must:

- Have a clinically typical appearance

[figure not shown]
- Have a PLA of ≥ 2
- Be a discrete lesion (no overlapping lesions)
- Not be covered with hair which, in the investigator's opinion, would interfere with the study medication treatment or the study evaluations (NB: the study medication may bleach hair)
- Not be in an intertriginous fold
- Not be on the eyelids
- Not be within 5mm of the orbital rim
- Not be pedunculated.

Record the approximate location of each target and non-target SK on the body chart in the CRFs. Number the target SK starting with 1 and proceeding up to 3 with no number omitted or reused. The target SKs on the face should be numbered 1 and 2, and the additional 1 SK on the neck and/or décolletage should be numbered 3. The non-target SKs should be numbered 4-7 starting with 4 and proceeding up to 7 with no number omitted or reused.

Aclaris Therapeutics, Inc. will provide the investigational site with standard circular templates and colored stickers that are to be used to identify the target and non-target SKs.

At Visit 1, the investigator and a HCP will identify the target and non-target SKs by placing 2 appropriately colored stickers approximately 180 degrees opposite each other with the target or non-target SK in the center of the area outlined by the provided circular template (Refer to [Figure 2](#). Figure not to scale):

Figure 2: Target and Non-Target SK Identification

Write the target or non-target SK number on one of the identification (ID) stickers. The ID stickers must be visible in the study photographs. The target and non-target SK #/ID sticker color relationships are:

- Target SK on face#1/white ID stickers
- Target SK on face #2/yellow ID stickers
- Target SK on neck or décolletage #3/green ID stickers
- Non-Target SK on the face, neck or décolletage #4/pink ID stickers
- Non-Target SK on the face, neck or décolletage #5/grey ID stickers
- Non-Target SK on the face, neck or décolletage #6/purple ID stickers
- Non-Target SK on the face, neck or décolletage #7/orange ID stickers

At each study visit a HCP from the investigational staff will confirm the location of each target and non-target SK using an appropriate combination of the Visit 2 hard-copy reference prints and the body charts. The staff member will identify the target and non-target SKs by placing 2 appropriately colored ID stickers, with the target or non-target SK number written on one sticker, approximately 180 degrees opposite each other with the target or non-target SK in the center of area outlined by the provided circular template.

10.1.1. Standardized Photography

At each study visit a qualified investigational center staff member will take standardized color photographs of each target and non-target SK.

The photographs are to document the location of the target and non-target SK and to assist with relocating the target and non-target SK and the target and non-target SK ID stickers must be visible in the photographs. The subject's identity will not be revealed in the study photographs. These photographs will also be used to document the treatment effects of A-101 40% over time.

At Visit 2, the photographs must be taken prior to the study medication application, 10 minutes post application, and 1-hour post application of A-101 40%. At Visit 5 and Visit 7, the photographs will be taken prior to study medication application, if applicable. At Visit 3 photographs must be taken 24 hours post application of A-101 40% on Visit 2.

Care must be taken to ensure the same lighting, background, subject positioning relative to the camera and camera settings are used for each photograph.

Sites will be provided with photography equipment and supplies necessary for obtaining the target and non-target SK photographs. Detailed instructions for obtaining and managing the photographs will be documented in the study specific Photography Manual and provided to the site at the study initiation visit.

10.1.2. Physician's Lesion Assessment (PLA)

The PLA is the investigator's assessment of the severity of the target and non-target SK at a particular time point. The investigator may refer to other evaluations (e.g., prior photographs) to assist with these assessments.

At Visits 1, 2, 3, 4, 5, 7, 10, and 11 the investigator will assess the target and non-target SK using the scale below and report the one integer that best describes the severity of the target or non-target SK. At Visit 2 and if applicable at Visit 5 and Visit 7, the investigator must complete the PLA prior to the study medication treatment.

Table 5: Physician’s Lesion Assessment Definitions

Grade	Descriptor
0	Clear: no visible seborrheic keratosis lesion
1	Near Clear: a visible seborrheic keratosis lesion with a surface appearance different from the surrounding skin (not elevated)
2	Thin: a visible seborrheic keratosis lesion (thickness \leq 1mm)
3	Thick: a visible seborrheic keratosis lesion (thickness $>$ 1mm)

All investigational site staff will receive training on the PLA Assessment Scale and be provided with a PLA Assessment Manual (refer to Appendix 2) that will be used as a reference tool during the conduct of the study.

In order for a subject to be eligible for screening and enrollment to the study, each target and non-target SK must have a PLA grade of \geq 2.

10.1.3. SK Dimensions

At Visit 1 and Visit 2 prior to study enrollment, the investigator will measure the diameter and thickness of each target and non-target SK using the ruler provided.

The investigator must measure the diameter of the longest axis of each target and non-target SK in millimeters (mm) as follows:

- Diameter (*i.e.*, the length of the longest axis)
- Thickness (height above the surrounding skin)

The PLA (the thickness) of the target and non-target SKs will be measured by the investigator at Visits 3, 4, 5, 7, 10, and 11. When the visit coincides with treatment (Visits 2, 5 and 7), the thickness must be measured prior to the application of study medication.

10.2. Subject Instructions

An investigational center staff member will dispense a Subject Instruction Sheet to each subject at Visit 1 (Refer to Appendix 1).

Throughout the study, the subjects should:

- Continue their routine cleansing regimen
- Continue their routine cosmetics and skin care products
- Avoid exposing the target and non-target SKs to excessive natural or artificial ultraviolet radiation (*e.g.*, sunlight, tanning beds) and use sunscreen on the target and non-target SKs, if excessive exposure cannot be avoided

- Avoid the use of self-tanning lotions and spray tans
- Bring the subject instruction sheet with them to each visit

On study visit days, the subjects should:

- When appropriate for the target and non-target SK locations, wear loose fitting clothing to the visit (Note: clothing that comes in contact with the study medication may be bleached)
- Starting with Visit 2, not apply any topical products to the target or non-target SKs within 12 hours prior to the visit (Note: routine cleansing products are allowed)
- After the completion of any study visit where a study medication treatment was performed DO NOT:
 - Wash/submerge the target or non-target SKs for at least 6 hours
 - Apply any topical products to the target or non-target SKs for at least 6 hours

10.3. Subject Satisfaction Assessment

Subjects will be asked to assess their level of satisfaction regarding the study medication treatment experience. The subject survey will be completed at Visits 2, 3, 6 (only if treated at Visit 5), 8 (only if treated at Visit 7), 10, and 11. (See Appendix 3)

10.4. Study Supplies

Aclaris Therapeutics, Inc. will provide:

- An appropriate ruler, or other instrument, for measuring the diameter and thickness of the target and non-target SKs
- Templates for use when identifying target and non-target SKs
- Equipment, supplies and training for taking standardized photographs

11. ASSESSMENT OF SAFETY

In addition to reporting adverse events throughout the study the investigator, a designated and appropriately trained HCP will perform the safety assessments according to the schedules noted below.

11.1. Vital Signs

Vital signs will be measured by a qualified staff member at Visit 1, Visit 2, Visit 5, Visit 7 Visit 10, and Visit 11. The following items will be measured:

- Body temperature
- Pulse rate
- Respiration rate
- Blood pressure (systolic and diastolic) after the subject sits quietly for at least 5 minutes
- Height (at Visit 1 only)
- Weight (at Visit 1 only)

Any measure that is, in the opinion of the investigator, abnormal AND clinically significant (CS) must be recorded as history if found prior to the first study medication treatment or as an AE if found after the first study medication treatment begins (Section 11.6).

A systolic blood pressure >140mm Hg or a diastolic blood pressure >90mm Hg is considered abnormal and therefore must be defined as CS or NCS on the CRFs.

11.2. Other Evaluations

11.2.1. Demographic/Medical History

At Visit 1, the investigator or designee will collect demographic information including date of birth, sex at birth, race, and ethnicity for each subject.

At Visit 1, the investigator must determine each subject's Fitzpatrick Skin Type and document appropriately on the subject's source document and CRF.

Table 6: Fitzpatrick Skin Type Scoring System

Skin Type Classification	Description
Type I	Always burns, never tans (pale white; blond or red hair; blue eyes; freckles)
Type II	Usually burns, tans minimally (white; fair; blond or red hair; blue, green, or hazel eyes)
Type III	Sometimes mild burn, tans uniformly (cream white; fair with any hair or eye color)
Type IV	Burns minimally, always tans well (moderate brown)
Type V	Very rarely burns, tans very easily (dark brown)

Skin Type Classification	Description
Type VI	Never burns, never tans (deeply pigmented dark brown to darkest brown)

11.3. Adverse and Serious Adverse Events

11.3.1. Definition of Adverse Events

An adverse event (AE) is any untoward medical occurrence in a subject that develops or worsens in severity during the conduct of a clinical study of a pharmaceutical product and does not necessarily have a causal relationship to the study drug. An adverse event can, therefore, be any unfavorable and unintended physical sign, symptom, or laboratory parameter that develops or worsens in severity during the course of the study, or significant worsening of the disease under study (or any concurrent disease), whether or not considered related to the study drug.

Accordingly, an adverse event could include any of the following:

- intercurrent illnesses
- physical injuries
- events possibly related to concomitant medication
- significant worsening (change in nature, severity, or frequency) of the disease under study or other preexisting conditions.
- drug interactions
- events occurring during diagnostic procedures or any washout phase of the study
- laboratory or diagnostic test abnormalities occurring after the start of the study (i.e., after screening and once confirmed by repeat testing) that results in the withdrawal of the subject from the study, requires medical treatment or further diagnostic work up, or is considered by the study investigator to be clinically significant.

The investigator must, for any target or non-target SK related AE, question the subject in detail to determine if there are any confounding factors (e.g., irritation by clothing or activity, sunburn) for any such AE.

The investigator should, when certain, report a diagnosis rather than the signs, symptoms or clinically relevant abnormal laboratory values associated with the AE. Otherwise, signs, symptoms or abnormal laboratory values may be used to describe the AE.

The investigator must start reporting non-serious AEs starting with the subject's first study medication treatment continuing through Visit 11.

11.3.2. Serious Adverse Event (SAE)

A serious adverse event is any untoward medical occurrence that at any dose results in one or more of the following:

- Results in death

- It is immediately life-threatening
- It requires in-patient hospitalization or prolongation of existing hospitalization
- It results in persistent or significant disability or incapacity
- Results in a congenital abnormality or birth defect
- It is an important medical event that may jeopardize the subject or may require medical intervention to prevent one of the outcomes listed above.

The term “life threatening” refers to an event in which the subject was at risk of death at the time of event; it does not refer to an event that hypothetically might have caused death if it was more severe.

Inpatient hospitalization is considered to have occurred if the subject is admitted to the hospital on an in-patient basis, even if released the same day. Prolongation of hospitalization is defined as an additional night stay in the hospital. Hospitalization for elective treatment of a pre-existing condition that did not worsen from baseline is not considered an AE.

Important medical events are those that may not be immediately life threatening, result in death or hospitalization, but are clearly of major clinical significance and may jeopardize the subject or require intervention to prevent one of the outcomes listed in the SAE definition above. These should also usually be considered serious. Examples of such events are intensive treatment in an emergency room or at home for allergic bronchospasm, blood dyscrasia or convulsions that do not result in hospitalization.

11.4. Relationship to Study Drug

The investigator will determine if there is a reasonable causal relationship between the study medication and an AE or not. The investigator will use her/his best medical judgment and consider all relevant factors (*e.g.*, temporal relationship, location of the event, the subject’s relevant medical history, concomitant therapies and concurrent conditions) to determine the relationship of the AE to the study medication. The investigator will define the relationship of an AE to the study medication by selecting one of the following categories:

Related – There is a reasonable possibility that there is a causal relationship between the study medication and the AE.

Not Related – There is not a reasonable possibility that there is a causal relationship between the study medication and the AE.

The term “reasonable causal relationship” means there are facts or arguments to suggest a causal relationship (International Conference on Harmonization (ICH) E2A).

11.5. Severity

The investigator must define the severity of each AE using the following definitions as a guideline. The investigator will consider the range of the possible severity of the event and identify the severity that is the most appropriate according to her/his medical judgment.

Intensity will be assessed according to the following scale:

- Mild - Awareness of sign or symptom, but easily tolerated
- Moderate - Discomfort sufficient to cause interference with normal activities
- Severe - Incapacitating, with inability to perform normal activities

11.6. Reporting Adverse Events

At each post enrollment visit, the investigator or designee will question the subject to elicit AEs using a non-directive question such as “Has there been any change in your health since the previous study visit?”

The investigator or designee will monitor the subject for at least 20 minutes after the Treatment Completion Time at Visit 2, and if applicable at Visit 5 and Visit 7 to elicit AEs in a similar manner.

If appropriate, based on the subject’s response to non-directed questioning regarding AEs, the investigator or designee will follow-up with directed questions and appropriate evaluations.

Non-serious AEs should be recorded starting with the subject’s first study medication treatment at Visit 2 and continuing through Visit 11.

All SAEs regardless of relationship to study medication must be collected and reported to Aclaris Therapeutics, Inc. from the time the Informed Consent is signed through Visit 11.

Upon becoming aware of a SAE the investigator must:

1. Take the appropriate medical action to ensure the subject’s safety
2. Immediately inform the Safety Monitor of the SAE:

[name]
Aclaris Therapeutics, Inc.
[name]
[name]
[contact]
Serious Adverse Event [contact]
Email: [contact]

3. Within 24-hours of becoming aware of the event, a SAE report form, an AE CRF and any other relevant information (*e.g.*, concomitant medication CRF, medical history CRF, laboratory test results) must be faxed to the SAE Fax line listed above.
4. Monitor and document the progress of the SAE until it resolves or, if not resolved after the subject’s last study visit, until in the opinion of the investigator the SAE reaches a clinically stable outcome with or without sequelae AND the investigator and Safety Monitor agree that the SAE is satisfactorily resolved.
5. Inform the Safety Monitor of SAE updates by telephone followed by an SAE form update sent by fax or by e mail.

6. Comply with the appropriate regulatory requirements and Aclaris Therapeutics, Inc. instructions regarding reporting of the SAE to the responsible Institutional Review Board (IRB) or Ethics Committee (EC).

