Numerous treatment options exist and include a plethora of destructive/ablative modalities such as liquid nitrogen cryotherapy, electrodesiccation, lasers of various wavelengths (ablative and non-ablative), radio-frequency ablation, and surgical removal by curettage or surgical excision. There is, however, a notable lack of well-controlled clinical trials comparing the efficacy, complications and complication rates of these treatments. There is great variability among practitioners in the methods employed using each of these techniques (*e.g.*, variability in contact time and method of freezing the lesions with liquid nitrogen) with great variability of the results. None of these treatments is, in fact, approved by the Food and Drug Administration (FDA) for the treatment of seborrheic keratosis. While these methods can be effective, many require specialized training and/or the use of expensive equipment, they are painful and may require anesthesia and/or analgesia, and they are often complicated by significant adverse outcomes. Both hypopigmentation and hyperpigmentation, which may be transient, but are often permanent, are common, as is scarring at the treatment site, and the typical post-surgical risks of bleeding and infection increase the risk that the result of the treatment of these lesions may be worse than the disease itself (Pierson DBC 2003) (Motley 2002) (McKee PH 2005).

Hydrogen peroxide (H₂O₂) is a compound that is ubiquitous in the environment. It is the simplest peroxide and a potent oxidizing agent commonly used in innumerable household goods including chlorine-free bleaches, general-purpose cleaning products, and disinfectants. Additionally, H₂O₂ has been employed as the oxidizing component in hair dyes, and has been used in oral hygiene products and tooth-whitening systems for many years. In industry, it is employed in the treatment of wastewater. In high concentrations, it is used in bleaching paper, pulp, and textiles. Clinically, in addition to its use as an oral topical agent noted above, H₂O₂ is widely employed at low concentrations (*e.g.*, 3%-6%) as a wound irrigant and topical antiseptic/disinfectant, and has been in use medicinally since its introduction into clinical practice by Richardson in 1858. (Schumb WC 1955) (Chan HP 2008) (Richardson, On Peroxide of Hydrogen, or Ozone, or Water as a Remedy: Continued from a Research Commenced in the

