A-101-SEBK-303 was a large open-label safety study in which subjects received up to 4 applications of A-101 40% Solution to SK lesions on their face, trunk or extremities.

A total of 147 subjects were enrolled and treated and 139 subjects (94.6%) completed the study. Five subjects withdrew consent and 3 subjects were lost to follow-up. The mean age was 68.4 years (range 35 to 94, 40.1% were at least 71 years old), 32.0% of subjects were male and 68.0% were female, and 93.9% of subjects were Caucasian. The most common Fitzpatrick skin types were 2 (48.3%) and 3 (32.0%).

At Visit 12 (Day 148) in the ITT population, 10.9% of subjects had all 4 target lesions judged to be clear on the PLA (PLA = 0), 18.4% had at least 3 of 4 target lesions judged to be clear, and 27.9% had all 4 target lesions judged to be clear or near clear (PLA ≤ 1). In the PP population, the PLA average per-subject percent of target lesions judged to be clear at Visit 12 was 28.2%.

TEAEs were reported for 25 (17.0%) subjects. The most frequently reported TEAEs were cough, seasonal allergy, and sinusitis (2.0% each). No TEAEs were reported as severe, no SAEs were reported, and no subject discontinued the study due to an AE or SAE.

LSRs reported were predominantly mild and most commonly included transient pruritus, stinging, crusting, edema, erythema, and scaling post-treatment that usually resolved by the next visit. Few lesions had LSRs at Visit 12.

There were no clinically significant changes during the study in laboratory evaluations or vital signs.

All three of the phase 3 studies described above demonstrated that treatment with A-101 (hydrogen peroxide) Topical Solution 40% was both effective and well-tolerated for the treatment of subjects with multiple seborrheic keratosis lesions of the trunk, extremities, and face.

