In the absence of a visible SK lesion (*i.e.*, a "stuck on," warty, well-circumscribed, often scaly lesion) the PLA grade should be "0" (Clear - no visible seborrheic keratosis lesion) even if the skin is not completely clear of other visible findings that are common on the normal, non-diseased skin of the subject such as signs of photo aging, pigmentary changes, erythema, roughness, scaling, etc. If there is uncertainty regarding the presence of an SK lesion, the treatment area may be palpated.

Please refer to the photo guide provided on the next pages for a PLA grade of "0".

[figure not shown]
If the identified area of skin contains a visible SK lesion, regardless of the size of that lesion, the PLA grade is NOT "0" and the procedure below should be followed to evaluate the lesion.

2. Measure the thickness of the SK lesion

The SK lesion should be examined with a suitable non magnifying examination light. Cross lighting may be used.

Once it has been determined that a visible SK is present, the thickness of the SK lesion should be measured at its thickest point using the ruler provided as illustrated below. The ruler should be gently placed on the non-lesional skin behind the SK lesion, perpendicular to the skin without creating a depression on the skin.

Examine the visible SK lesion on a line parallel with the plane of the surrounding non-lesional skin and observe the ruler markings at the thickest point of the lesion.

PLA Grade 1:

The SK lesion should be assigned the PLA grade of "1" (Near Clear: a visible SK lesion with a surface appearance different from the surrounding skin (not elevated)) if:

- The SK lesion is macular (not palpable), and therefore has no elevation.
- The SK lesion has an elevation that is less than 0.5mm (*i.e.*, the 0.5mm mark is completely visible behind the SK lesion).

Please refer to the photo guide provided on the next pages for a PLA grade of "1".

PLA Grade 2:

If the SK lesion covers any part of the 0.5mm mark and does not completely cover the 1mm mark the SK lesion PLA grade should be: "2" (Thin: a visible seborrheic keratosis lesion (thickness ≤ 1 mm)).

PLA Grade 3:

If the SK lesion completely covers the 1mm mark the PLA grade should be: "3" (Thick: a visible seborrheic keratosis lesion (thickness > 1 mm)).

[figure not shown]
Please refer to the photo guide provided on the next pages for grades of "2" and "3".

SK PLA Training Manual
January 12, 2016

[figure not shown]
Photo guide

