### **3.8 SAFETY ANALYSIS**

The safety and tolerability of the investigational products will be determined by reported AEs, and vital signs.

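### No structured lesion-by-lesion grading of local skin sequelae is planned; unprompted AE reports and ungraded photographs are the only sources

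*Protocol*

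**What the plan says.** **Capture of local effects.** Under Protocol 11.6, "the investigator or designee will question the subject to elicit AEs using a non-directive question such as" one about a change in health since the last visit. After that, where appropriate and "based on the subject’s response to non-directed questioning regarding AEs, the investigator or designee will follow-up with directed questions and appropriate evaluations". Non-serious AEs are recorded from the first treatment through Visit 11.

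**Safety analysis.** SAP 3.8 states: "The safety and tolerability of the investigational products will be determined by reported AEs, and vital signs". SAP 3.8.1 tabulates treatment-emergent AEs (TEAEs) by MedDRA class and preferred term, and describes AE assessment as ending 30 days after the last treatment. SAP 2.4.3.1 instead repeats the protocol's rule of collection through Visit 11.

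**Lesion-level assessments.** Table 3 schedules PLA and dimensions at Visits 1, 2, 3, 4, 5, 7, 10 and 11, and photographs of every lesion at all visits. Protocol 10.1.1 gives documentation of treatment effects over time as one use of the photographs. Neither document plans to grade or analyse them.

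**The PLA.** The training manual in Appendix 2 leaves texture, size, shape and color unscored. Grade 0 is given when no seborrheic keratosis (SK) is visible, "even if the skin is not completely clear of other visible findings that are common on the normal, non-diseased skin of the subject". Its examples are "signs of photo aging, pigmentary changes, erythema, roughness, scaling, etc".

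**Satisfaction.** The End of Study form, used at Day 85 and Day 113, asks about satisfaction with the appearance of the treated skin (item 4) and bother from the treated SKs (item 8). Protocol 12 correlates each satisfaction scale with per-subject averaged PLA results.

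**Background.** Of existing destructive treatments, the Introduction says: "Both hypopigmentation and hyperpigmentation, which may be transient, but are often permanent, are common, as is scarring at the treatment site". Of the open-label study 303 it says: "LSRs reported were predominantly mild and most commonly included transient pruritus", where LSR is the local skin reaction record.

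**The concern.** Every lesion in this study is on the face, neck or décolletage, where a residual mark shows. The Introduction treats pigment change and scarring as important harms of competing methods. Yet no scheduled item asks the investigator to record whether a treated site is lighter, darker, red or scarred.

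Two things are at stake.

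- **The rate of local effects.** A mark becomes data only if the subject volunteers it or the investigator decides that it is an AE. The documents do not say whether expected reactions count as AEs, so sites may decide differently. A low reported rate would be hard to interpret.
- **The PLA–satisfaction analysis.** The PLA measures presence and thickness of the SK; items 4 and 8 ask how the skin looks. A subject whose lesions are all graded clear may still dislike a color change. In the planned correlation this would appear as weak agreement, with no collected variable designed to explain it.

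**Working it through.** The plan gives no figure to reproduce on this point. The sample size of 30 is stated without a precision target, and the study is descriptive. The check therefore sets the possible sources side by side and then adds arithmetic on what 30 subjects can show.

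**1. Which source could give a lesion-level rate of sequelae?**

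- *AE reports (Protocol 11.6, SAP 3.8.1):* counted per subject and unprompted. Severity under Protocol 11.5 is defined by tolerability and interference with activity, so a conspicuous but painless mark would tend to rate as mild.
- *PLA (Appendix 2):* per lesion, but color and texture are not scored, and Grade 0 is compatible with some residual pigment change or erythema.
- *Dimensions (Protocol 10.1.3):* diameter and thickness only.
- *Photographs (Protocol 10.1.1):* per lesion, at every visit, but no grading planned.
- *End of Study form (Appendix 3):* per subject, with no question on the reason for dissatisfaction.

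None of these yields a solicited lesion-level rate.

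**2. Do the sponsor's earlier studies suggest that AE lists capture local reactions?** In study 303 the most frequent TEAEs were cough, seasonal allergy and sinusitis, at 2.0% each. Pruritus, stinging, crusting, edema, erythema and scaling are described separately as LSRs. In study 301 the leading TEAEs were also non-skin terms, while hyperpigmentation appears among investigator-reported LSRs. The two were kept apart, and the leading AE terms alone would not have shown the local reactions. LSR rates are not given, so the size of the difference is unknown.

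**3. AE window.**

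- SAP 3.8.1, last treatment on nominal Day 1, 15 or 29: 1 + 30 = Day 31; 15 + 30 = Day 45; 29 + 30 = Day 59.
- Earliest Visit 10: 85 − 7 = Day 78.
- Under SAP 3.8.1, a sequela first reported at Visit 10 or 11 could fall outside the window. Under Protocol 11.6 and SAP 2.4.3.1 it is collected.

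**4. What a zero count means.**

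- Exact two-sided 95% upper bound for 0/30: 1 − 0.025^(1/30) = 11.6%, with full capture.
- If only a fraction *c* of affected subjects is recorded, the bound becomes 11.6%/*c*. For *c* = 0.75, 0.50 and 0.25 (assumptions) it is 15%, 23% and 46%. The lower limit stays at 0% throughout.
- From the other side, assume a true subject-level rate of 20%, so 30 × 0.20 = 6 affected subjects. With capture of 25% to 75%, 1.5 to 4.5 would be recorded. The chance of recording none is (1 − 0.20*c*)^30, which is 21% at *c* = 0.25 and 0.8% at *c* = 0.75.

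**5. What structured grading would give.**

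- Lesions: 30 × 3 = 90 to 30 × 7 = 210.
- Subject level, exact 95% intervals: 3/30 gives 2.1% to 26.5%; 6/30 gives 7.7% to 38.6%.
- Lesion level, with *m* lesions per subject: effective *n* = 30*m*/(1 + (*m* − 1)ICC); half-width = 1.96√(0.1 × 0.9/*n*), for an assumed rate of 10% and assumed intraclass correlation (ICC) of 0 to 0.5.
  - *m* = 3: effective *n* 90 to 45, half-width 6.2 to 8.8 points.
  - *m* = 7: effective *n* 210 to 52.5, half-width 4.1 to 8.1 points.

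The rate would be estimable, though imprecisely.

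**The case against.** The strongest reply is one of scope. This is a 30-subject, descriptive post-marketing study whose objective is satisfaction, and three phase 3 studies already reported LSRs. Not repeating that assessment is a defensible choice. This stands as an argument about priority. It does not remove the gap in the satisfaction analysis, because a driver of appearance scores matters most in a study of those scores.

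Stronger readings are tempting, and the documents do not support them.

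- *That lesions are never looked at for sequelae.* Standardized photographs of each lesion at every visit are a lesion-level record. They are ungraded, but they exist.
- *That AEs depend wholly on the subject speaking up.* Protocol 11.3.1 defines an AE to include unfavorable physical signs, the investigator examines each lesion at the PLA visits, and subjects are monitored for at least 20 minutes after each treatment. An investigator may report a mark unprompted. Nothing requires a systematic look.
- *That no rate will be available.* The TEAE tables give a subject-level rate of reported events.
- *That the manual tells graders to disregard treatment damage.* Its wording concerns findings common on the subject's normal skin and does not name scarring. What is firm is that color and texture are not scored.
- *That sequela grading would explain dissatisfaction with one cleared lesion.* Satisfaction is collected once per subject across 3 to 7 lesions, so only a subject-level link is possible.
- *That the true rate is about 23%.* That figure is an upper bound under an assumed 50% capture.

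The separate satisfaction analysis plan and the post-treatment questionnaire listed in SAP 2.4.2.3 are not in the text available here, so their content cannot be judged. The questionnaire is for use after each treatment, which places it at Visits 3, 6 and 8 (to Day 36). A separate plan could draw on AE records or photographs, but not on a graded sequela variable that Table 3 does not schedule.

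**Conclusion.** The point holds in a limited form. No structured lesion-level grading of local sequelae is planned; the sources are unprompted, subject-level AE reports and ungraded photographs, and the PLA does not score color or texture. The reported rate of local effects may therefore be too low and may vary by site, and a plausible reason for low scores on items 4 and 8 in subjects graded clear goes unmeasured.

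The one firm number is the 11.6% upper bound for 0 of 30, which assumes full capture. The degree of under-reporting cannot be estimated from these documents. That sequelae lower satisfaction is plausible but not shown in them.

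The conflict over the AE window is textual and needs no assumption: SAP 3.8.1 disagrees with Protocol 11.6 and with SAP 2.4.3.1. It bears directly on late sequelae.

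This is an inexpensive improvement to a descriptive study. It does not invalidate the primary summary of satisfaction.

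**What to change.** 1. **Collect.** At Visits 10 and 11, when the investigator already grades each lesion, record per lesion the presence and severity of erythema, hypopigmentation, hyperpigmentation and scarring. Define the severity levels in a line each, and judge them against the surrounding skin so that background photo-aging is not counted.
2. **Tabulate.** In SAP 3.8, report these at Day 85 and Day 113 per lesion and per subject, by face versus neck/décolletage. Any interval at lesion level should allow for clustering within subject.
3. **Link.** Describe items 4 and 8 by presence of any sequela at subject level. No new composite outcome is needed.
4. **Reconcile.** Bring the AE window in SAP 3.8.1 into line with Protocol 11.6 and SAP 2.4.3.1, so that sequelae first reported at Day 85 or Day 113 are counted.

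The cost is one extra CRF page at two existing visits, brief instruction for the graders, a short amendment and one SAP table. No visit, staff or procedure is added. Reported local-effect rates will be higher than with unprompted reporting, and the report should say that they were solicited. Grading at more visits, or for more signs, is not needed for this purpose.
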